15.7 Follow-up

The following assessments will be completed via a telephone call within five days after the procedure:

• Adverse Events – any adverse events that occurred since the day of the procedure.

If no adverse events have occurred, it will be documented in the CRF accordingly.

15.8 Study Population

A total of 50 subjects will be enrolled in the study.

15.8.1 Inclusion Criteria

- Subjects older than 18 years (adults).
- Subjects able to provide informed consent.

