Key Protocol Contributors	[name], MBChB, MRCS
	Email: [contact]
	[contact] [name]

5 Study Summary

Full Study Title	Evaluation of the GRI gentleheel® incision device for adult fingertip blood sampling - intended use extension
Internal ref. no. (or short title)	Evaluation of the GRI gentleheel® incision device for adult blood sampling.
Study Design	Prospective, interventional, non-randomised, single-centre study.
Study setting	Single site
Planned Size of Sample	50
duration	5 days
Planned Study Period	4 weeks for the purpose of recruitment
Research Question/Aim(s)	Can GRI gentleheel® incision device be safely used by lay members of the adult population for the purpose of capillary blood sampling from the fingertip.

6 Funding and Support

FUNDER	FINANCIAL AND NON FINANCIAL SUPPORT GIVEN
Mowgli Innovation	Financial support
Mowgli Innovation	Non-financial support (Sponsor)

ROLE OF STUDY SPONSOR AND FUNDER

The role of the study funder is to provide financial support to the study. The sponsor takes on ultimate responsibility for the initiation and management the research, providing the facilities in which the study patients will take part in the trial. The sponsor will ensure primary responsibility for ensuring that the design of the study meets appropriate standards and that arrangements are in place to ensure appropriate conduct and reporting.

ROLES AND RESPONSIBILITIES OF STUDY MANAGEMENT COMMITEES/GROUPS & INDIVIDUALS

The Principle Investigator and the study co-ordinator will be responsible for patient recruitment, and randomisation, data collection and analysis, annual progress report as well as final report preparation. Patient & Public Involvement Groups will not be involved in the design and implementation of the study.

7 Protocol Contributors

IRAS Number: 311621

The study sponsor (Mowgli Innovation) will be involved in the review of the study protocol, data analysis and interpretation as well as manuscript writing and dissemination of the results. The key protocol contributors, the principal investigator and the study co-ordinator will assist the study sponsor in these tasks, however, the final decision regarding the study design, conduct of the study, data collection and analysis, annual progress report and final report preparation lies with the principle investigator.

Key Protocol Contributor	[name], MBChB, MRCS	
	Email: [contact]	
	[contact] [name]	

8 Contents

1	Title	Page	2	2
2	Rese	earch	Reference Numbers	2
3	Sign	ature	Page	3

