12.3 Proposed Solution

IRAS Number: 311621

Our solution to the problem is to modify the use of a pre-existing device on the market (gentleheel®) to address the shortcomings of blood capillary sampling devices with regards to obtaining an adequate volume of blood. The gentleheel® device, is a heel incision device designed for use in new-born blood sampling. This device is CE-marked and FDA approved. It offers a safe and efficient way of acquiring blood samples from the heels of new-borns and toddlers. The device is engineered with the following features to ensure ease of use and minimal discomfort for the patient:

- Ergonomic design for improved handling.
- Multiple visual indicators reinforce incision site.
- Incision devices are less traumatic than punctures.
- Tri-bevel blade generates a smoother, less traumatic incision.
- Hardened stainless steel blade improves incision accuracy.
- Permanent blade retraction minimizes possible reuse or injury.
- Welded plastic casing prevents accidental exposure to the blade.

The fundamental difference between gentleheel® and other devices is the greater volume of blood that can be extracted from a single finger prick. This is due to the type of lancet and the way it is deployed. In contrast to traditional devices that use a needle as a lancet that punctures the skin, gentleheel ® utilises a blade, creating a 3.0 mm area of dermal bleeding, resulting in improved blood flow, allowing for increased volume of blood to be collected with the potential to reduce the aforementioned limitations with needle-based lancets. The incision depth is 2.0 mm, in accordance with safety limits recommended by the World Health Organization (WHO) guidelines on the use of capillary blood sampling devices (6).

This device, however, is only licensed for use by healthcare professionals on the heels of new-borns and toddlers. The intention of this study is to extend the utility of this device by investigating its use in capillary blood sampling from adult fingertips.

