12.4 Investigational Device

IRAS Number: 311621

This section shows gentleheel® device and contains a schematic of the mechanism of action.

Figure 1: Picture of the gentleheel® device model Toddler.

[figure not shown]

Figure 2: Schematic drawings showing from left to right the removal of the trigger lock.

[figure not shown]

Figure 3: Schematic drawings showing from left to right the sweeping motion of the tri-bevel stainless steel blade after the blade is deployed.

13 Research Question/Aims

Can gentleheel® incision device be used by lay members of the public without intervention from medically qualified practitioners for the purpose of capillary blood sampling in the fingertip?

14 Study Objectives

This clinical investigation is designed to collect information related to the performance and safety of this device during blood sampling in adult fingertips.

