16.3 Analysis Method

IRAS Number: 311621

All data will be anonymised prior to analysis.

The statistical analysis will be done on the ITT population. In case more than 10% of patients present major violations to the protocol (defined as any deviation which may significantly impact the evaluation of the endpoints), primary endpoints analysis will be re-assessed and documented appropriately.

Descriptive statistical data will be used to summarize the characteristics of subjects at the time of inclusion (demographics, baseline and procedure data).

The primary and secondary objectives will be presented as a proportion with 90% confidence intervals (CIs). For other objectives, quantitative variables will be summarized by the number of patients (n), mean, standard deviation (SD) and range; qualitative variables will be summarized by frequency and percentage of patients; rates will be summarized by the numerator, denominator, rate, and its 90% CI. Descriptive statistics only will be provided for AE data.

A complete adverse event description will be done: total number of events and number of patients with at least one of the respective categories AEs, ADEs, SAEs, SADEs, USADEs. Investigation Assessments

17 Participating Investigator and Site

One investigational site in the United Kingdom will be chosen for this study. This will take place at King's College London, in a dedicated research facility which routinely carries out blood sampling related studies.

The Principal Investigator is experienced in the field of phlebotomy and capillary blood sampling and collection. All training on how to use the gentleheel® device will be provided to the Investigator by the Sponsor of the study. A Study Coordinator will be available to ensure the data is collected, and any immediate adverse events noted.

18 Investigation Handling Procedures

The investigational device will be provided to the site by the sponsor. Each device will be entered and tracked on the Device Accountability Log. Once an investigational device is used, it should be discarded per the investigational site's disposal procedure. All devices are one-time use only. The devices should be kept in a secure location, in a cool, dry place.

19 Anticipated Adverse Events

Adverse events that may possibly be caused by, or associated with, the use of the gentleheel® for capillary blood sampling in adult fingertips include:

- Fainting during the incision procedure.
- Pain during and after the incision procedure.

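### The aim is use by lay people, but no eligibility criterion or listed data item separates lay users from people trained in blood collection

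*Protocol*

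**What the plan says.** **Who the question is about.** The Study Summary (Section 5) asks whether the device can be "safely used by lay members of the adult population for the purpose of capillary blood sampling from the fingertip". Section 13 narrows this to a device "used by lay members of the public without intervention from medically qualified practitioners". Section 12.3 gives the background: the device is "only licensed for use by healthcare professionals on the heels of new-borns and toddlers".

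**Who operates it.** Under Section 15.3 each participant makes two incisions, one on the middle and one on the ring finger. Section 15.5 has participants collect the blood themselves, following written instructions.

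**Who may enter.** Section 15.8.1 has two inclusion criteria: being over 18, and "Subjects able to provide informed consent". The exclusions in 15.8.2 cover medical conditions, coagulation-affecting medicines, pregnancy, needle anxiety, concurrent studies and recent blood loss, plus an investigator's catch-all. The synopsis (Section 23) adds cognitive impairment. The text shown does not define a lay user.

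**What is recorded and analysed.** The flow chart lists demographics, medical history and concomitant medication. Table 1 lists finger, side, volume and pain. The analysis population (16.2) is everyone who meets the inclusion criteria, consents and is willing to take part.

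**The concern.** When participants are the operators, eligibility decides whose skill is being tested. A site that followed 15.8.1 and 15.8.2 to the letter could enrol a nurse, a phlebotomist, a medical student, or an employee of the site or sponsor. That person would enter the same proportion as a member of the public.

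The result would then be read as evidence on unaided lay use, although part of it came from people who are not lay. An analysis plan cannot be relied on to repair this: it cannot change who was enrolled, and it can separate the two groups only if their status was recorded.

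**Working it through.** **Step 1: does any clause restrict or identify lay status?**

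| Place | What it covers | Reaches lay status? |
|---|---|---|
| 15.8.1 and synopsis, inclusion | Age, capacity to consent | No |
| 15.8.2 and synopsis, exclusion | Medical, medication, anxiety, other study, blood loss; cognition (synopsis only) | No |
| 15.8.2, catch-all | Conditions that could adversely affect participation | No: skill in taking blood is not such a condition |
| 16.2, analysis population | Inclusion met, consented, willing | No |
| 16.3, re-assessment if over 10% have major violations | Protocol deviations | No: enrolling a phlebotomist breaks no rule |
| Flow chart and Table 1 | Demographics, history, medication; finger, side, volume, pain | Occupation and previous lancing not named |

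**Step 2: the plan's own figure.** 50 subjects × 2 incisions = 100 draws, as stated in 16.1. Section 16.1 gives no assumed proportion or target precision, so there is no planned half-width to reproduce. Adding a lay-user criterion leaves the 50 and the 100 unchanged.

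**Step 3: how large could the effect be?** The protocol gives no success rates by type of user and no expected share of trained participants, so every share and rate here is assumed.

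Bias = (trained share) × (success rate in trained − success rate in lay users)

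| Trained share | Gap in success rate | Bias |
|---|---|---|
| 10% | 5 points | 0.10 × 5 = 0.5 points |
| 20% | 10 points | 0.20 × 10 = 2 points |
| 20% | 20 points (75% vs 95%) | 0.20 × 20 = 4 points (75% observed as 79%) |
| 20–30% | 30 points (60% vs 90%) | 6 to 9 points |
| 50% | 20 points (75% vs 95%) | 0.50 × 20 = 10 points (75% observed as 85%) |

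**Step 4: compare with the planned interval.** The plan uses a two-sided 90% CI. With n = 50 subjects and an assumed p = 0.75:

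half-width = 1.645 × √(0.75 × 0.25 / 50) = 0.101, about 10 points.

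Using n = 50 amounts to treating a subject's two draws as fully correlated. If all 100 draws were independent, it would be 1.645 × √(0.75 × 0.25 / 100) = 0.071, about 7 points.

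With small gaps and shares the bias is well inside the interval. With a 20-point gap it matches the 10-point half-width only when half the sample is trained. Whatever its size, the interval reflects sampling error and would not reveal it.

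**The case against.** **The formal objectives do not mention lay users.** Sections 14 and 14.1 and the synopsis objective and intended use speak of adults: volume after one lancing, pain, and safety. Section 12.3 describes the extension as one to adult fingertips, which is new for every user because the present licence covers infant heels. This stands. A reader might infer that data from professionals would be worthless. They would not be: they inform volume, pain and safety at the new site. The limit is on the lay-use inference, which Sections 5 and 13 still make the question of the study.

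**The device may matter more than the hand.** Section 12.3 attributes the larger volume to the blade and its deployment, Section 12.2 links volume to lancet design, and incision depth and length are fixed. This also stands as a reason not to assume a large gap. Sections 12.2 and 15.5 do show that handling counts (placing the base flush, wiping the first drop, not squeezing hard), so a gap of zero is not established either.

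**No document says trained people will be recruited.** A reader might infer from the site, "in a dedicated research facility which routinely carries out blood sampling related studies", and the 4-week recruitment period that staff would be the easiest volunteers. Section 17 describes the facility, not the source of participants, so that inference is not supported.

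**The case report form is not shown.** It may itemise occupation under demographics. Hence the point is that recovering lay status is not assured, not that it is impossible.

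None of this supplies the missing criterion.

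**Conclusion.** The gap is real: the aim and research question concern lay users who operate the device themselves, and no eligibility criterion, listed data item or analysis rule in the protocol restricts or identifies them. Confidence in that is high.

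Two stronger readings should not be drawn. One is that any consenting adult may enter: a long list of exclusions applies, though none bears on lay status. The other is that the result will be inflated: the direction is plausible, but the documents give neither a trained share nor a difference by user type. The illustrated bias runs from 0.5 to 10 points and depends wholly on assumed values; wider assumptions would give a wider range. Any effect on pain or adverse events is conjecture.

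This should be fixed before enrolment. It does not invalidate the volume and pain results as statements about adults.

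**What to change.** 1. Add one exclusion to 15.8.2 and to the synopsis list: *qualified or student healthcare professionals, phlebotomists, others professionally trained in blood collection, and employees of the sponsor or the investigational site*.
2. State that lay people who already self-lance, for example for glucose, remain eligible. The words *professionally trained* keep the exclusion from catching them.
3. Name occupation and previous self-lancing (yes/no) among the demographic items, so that lay status can be verified.

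The cost is one line in two places, one clarifying sentence and two data items. The sample size does not change. The downside is slightly slower recruitment at an academic site.

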15.8.2 Exclusion Criteria

- Subjects younger than 18 years.
- Subjects unable to provide informed consent.
- Subjects who may be dehydrated.
- Subjects diagnosed with poor peripheral circulation from other causes.
- Subjects who present with a callus, skin ulceration, or blister at the intended puncture site.
- Subjects with thrombocytopenia and/or Platelet abnormalities.
- Subjects diagnosed with peripheral edema. Pregnancy or breastfeeding (self-reported).
- Confirmed or suspected malignant cancer.
- Anxiety with needles or finger pricks.
- History of blood borne infection (e.g., HIV, hepatitis B or C, syphilis, malaria, babesiosis, brucellosis, leptospirosis, arboviral infections, relapsing fever, T lymphotropic virus Type 1, Creutzfeldt-Jakob disease).
- Currently participating in another study.
- Donation or loss of 400 mL or more of blood within 4 weeks prior to the start of the study.
- Any other condition that in the Investigator opinion may negatively influence Subject's participation in the study.
- Intake of medicines that affect blood coagulability (including anticoagulants such as vitamin K, antivirals and anticoagulants such as heparin, aspirin, thrombin inhibitors, vitamin K antagonists).

15.9 Withdrawal Criteria

IRAS Number: 311621

Patients have the right to withdraw from the study at any time and for any reason without prejudice to their future medical care by the investigation team or investigation site. The Investigator will record all information regarding the subject discontinuation. A patient may be

withdrawn from the study for the following reasons, and data until the date of withdrawal will be recorded in the Case Report Form (CRF):

- Subjects may choose to withdraw from the study under the terms of the Declaration of Helsinki and their consent documentation without having to give a reason;
- Any unanticipated adverse event which is, in the opinion of the Investigator, related to the treatment and will endanger the well-being of the patient if treatment is continued;
- Development of any intercurrent illness(es), infection or condition(s) that might interfere with the protocol;
- Non-compliance with the clinical investigation procedures deemed by the Investigator to be sufficient to cause discontinuation;
- Any problem deemed by the Investigator to be sufficient to cause discontinuation.

16 Statistical Considerations

16.1 Sample Size

Considering the design and objective of this investigation, the nature of the results needed to conclude on the safety and performance of gentleheel® as incision device for adult fingertips, and the fact that the device is already CE-marked as heel incision device for new-born sampling, the inclusion of 50 subjects in the investigation, a 2 incisions per subject, which will result in 100 blood draws to be assessed, appears therefore sufficient to obtain conclusive findings. This was based on the precision of the 90% CI for the primary objectives as this is a single-arm study. Under this approach, no statement of power is required and alpha = 0.10 will be used as the CI specified as a two-sided 90%.

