15.3 Investigation Design

IRAS Number: 311621

A sample size of 50 patients will be used. Each patient will perform two separate incisions on the middle and ring fingers, resulting in 100 blood draws. During the procedure, the following data will be documented:

- the location of the incisions (which finger middle/ring and which side of the fingertip ulnar/radial).
- the volume of blood obtained from each incision;
- the pain level experienced for each incision;

After appropriate explanation of the procedure to the patient, he/she will sign the Informed Consent Form to confirm that their participation in the study is voluntary. All required data as per the CRF will be obtained and the patient will then collect blood from 2 incisions on his/her fingertips.

All collected blood samples will be used for volume measurement and discharged afterwards. Following the blood collection from all 2 incisions, the patient will be appropriately monitored, until he/she leaves the investigational site. Any adverse event if presented will be documented before the patient leaves the investigational site.

Please see Table 1 for an overview of the data being collected for each subject on the day of the blood collection procedure.

Table 1: Overview of the data to be collected for each subject in the day of the blood collection procedure.

Incision #	Finger identification (middle/ring)	Incision position (radial/ulnar)	Volume of blood collected (µI)	Pain level (0 to 10)
1				
2				

Within 5 days of procedure, a follow-up telephone call will take place in order to assess if any adverse events occurred.

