22.1 Adverse Events and Device Deficiency Recording on the CRF

All AE must be reported for each patient with a full description, including the nature, the date of onset and resolution, the determination of seriousness, the severity, the action taken, the corrective treatment and the relationship to the device and/or procedure assessed by the Investigator. All investigational device deficiencies will be documented on the CRF and reported to Sponsor.

23 Protocol Synopsis

Title of the investigation: Evaluation of the GRI gentleheel® incision device for adult blood sampling Intended Use Extension				
Objective:	The objective of the proposed clinical investigation is to evaluate the safety and performance of the gentleheel® incision device for capillary blood sampling in adults' fingertips.			
Intended Use:	The gentleheel® device as a fingertip incision device intended for blood sampling in adults.			
Investigational Device:	gentleheel® model Toddler, Blue Incision depth 2.00 mm Incision length 3.00 mm			
Investigation Design:	Prospective, interventional, non-randomized, single-centre			
Participating Sites:	1 site in the UK			
Planned Number of Patients:	50 patients			
Sample size	100 blood draws, 2 finger incisions per patient			
Participation Duration:	Procedure: 20 minutes Follow-up: 5 days (Telephone Call)			
Total estimated duration of the investigation:	1 Month			
Outcomes:	Primary Objectives:			
	 Determine the capillary blood volume collected after a single lancing of the fingertip. Assessment of pain during finger incision using the 0-10 Numerical Pain Rating Scale Secondary Objectives: Adverse events. 			
Inclusion Criteria:	Subjects older than 18 years (adults)Subjects able to provide informed consent			

Exclusion Criteria:

- Subjects younger than 18 years
- Subjects unable to provide informed consent
- Subjects with cognitive impairment which is sufficient to adversely affect the participants understanding of the study, their ability to respond to patient questionnaires or their ability to cooperate with post-procedure assessment.
- Subjects who may be dehydrated
- Subjects diagnosed with poor peripheral circulation from other causes
- Subjects who present with a callus, skin ulceration, or blister at the intended puncture site
- Subjects with thrombocytopenia and/or Platelet abnormalities
- Subjects diagnosed with peripheral edema. Pregnancy or breastfeeding (self-reported)
- Confirmed or suspected malignant cancer

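### The 90% CI precision argument counts 100 blood draws without allowing for two draws per subject; intervals that treat the draws as independent would be too narrow

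*Protocol*

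**What the plan says.** Protocol Section 15.3 sets the structure: "Each patient will perform two separate incisions on the middle and ring fingers, resulting in 100 blood draws". Volume and pain are recorded for each incision. Section 15.8 gives the number of people: "A total of 50 subjects will be enrolled in the study".

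Section 16.1 moves from subjects to draws when it argues that the size is adequate: "a 2 incisions per subject, which will result in 100 blood draws to be assessed, appears therefore sufficient to obtain conclusive findings". The stated basis is precision: "This was based on the precision of the 90% CI for the primary objectives as this is a single-arm study". No power is claimed, and alpha is set at 0.10 two-sided. No target half-width, expected proportion or within-subject correlation is given.

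The unit called the sample differs across the document. The Study Summary (Section 5) gives a planned sample of 50. The sample size row of the synopsis (Section 23) reads "100 blood draws, 2 finger incisions per patient", in a separate row from the planned 50 patients.

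For the analysis, Section 16.3 says "The primary and secondary objectives will be presented as a proportion with 90% confidence intervals (CIs"). It does not say whether the denominator is draws or subjects, or how the interval is calculated. The only analysis population, in Section 16.2, is defined by subject.

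**The concern.** Both draws from a subject come from the same circulation, the same handling of the device and the same session, and the same person rates the pain of each. Positive correlation between the two results is the reasonable expectation, above all for self-rated pain. A second draw from a subject already sampled then adds less information than a draw from a new subject, and 100 draws carry the precision of somewhere between 50 and 100 independent observations.

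This matters because the study has one arm, no hypothesis test and no power statement. The 90% CI is its only inferential output and the stated reason for its size. A reader who takes 100 as the sample will expect more precision than the design may deliver. An analyst who follows the most natural route through the text, a proportion of 100 draws with a standard 90% interval, will report intervals whose coverage is below 90% whenever the correlation is positive.

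**Working it through.** **Inputs from the protocol.** 50 subjects (Section 15.8); 2 incisions per subject, so 50 × 2 = 100 draws (Section 15.3), which reproduces the protocol's count; two-sided 90% interval, so z = 1.645 (Section 16.1). The protocol prints no half-width, so there is no precision figure to reproduce.

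**Assumptions.** The proportion p and the intraclass correlation (ICC) between a subject's two draws are not given. I take p = 50%, where the interval is widest, and p = 80%, and vary the ICC from 0 to 1. The true ICC may differ between volume and pain.

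**Formulas, with m = 2 draws per subject.**

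- Design effect = 1 + (m − 1) × ICC = 1 + ICC
- Effective n = 100 / (1 + ICC)
- Half-width = 1.645 × √[p(1 − p) / effective n]
- True coverage of an interval that ignores the pairing = 2Φ(1.645 / √(1 + ICC)) − 1

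**End points at p = 50%.** With independent draws: 1.645 × √(0.25/100) = 8.2 points. With ICC = 1, equivalent to 50 observations: 1.645 × √(0.25/50) = 11.6 points. Ratio: √2 = 1.41.

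| Assumed ICC | Effective n | Correct width ÷ naive width | Half-width, p = 50% (points) | Half-width, p = 80% (points) | True coverage of naive 90% CI |
|---|---|---|---|---|---|
| 0 | 100 | 1.00 | 8.2 | 6.6 | 90.0% |
| 0.1 | 90.9 | 1.05 | 8.6 | 6.9 | 88.3% |
| 0.3 | 76.9 | 1.14 | 9.4 | 7.5 | 85.1% |
| 0.5 | 66.7 | 1.22 | 10.1 | 8.1 | 82.1% |
| 0.7 | 58.8 | 1.30 | 10.7 | 8.6 | 79.3% |
| 1.0 | 50 | 1.41 | 11.6 | 9.3 | 75.5% |

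**Checks without the normal approximation.** Clopper-Pearson 90% limits at 80% observed are 72.3% to 86.3% for 80/100 and 68.4% to 88.7% for 40/50. A beta-binomial simulation of 50 pairs with ICC 0.5 (40,000 runs, Wilson interval on 100) gave coverage of 83.4% at p = 50% and 81.5% at p = 80%, close to the 82.1% in the table.

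**For scale.** Matching the precision of 100 independent draws would take 50 × (1 + ICC) subjects: 65 at ICC 0.3, 75 at 0.5 and 100 at 1.

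**The case against.** The strongest reply is that the protocol never says the draws will be analysed as independent. Section 16.3 names no denominator and no interval method, the population in Section 16.2 consists of subjects, and the summaries for other objectives count patients. A subject-level or pair-adjusted interval would be fully consistent with the text, and the variance method may lie in a statistical analysis plan that is not shown. This stands. A reader might infer that the reported intervals will be too narrow; the document supports only that they would be if 100 draws were treated as independent.

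Three other stronger readings also fail:

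- It is tempting to say that the claim of conclusive findings rests on the count of 100 alone. Section 16.1 also cites the design, the objective, the existing CE mark and the 50 subjects, and it states the two incisions per subject openly.
- One might argue that the second incision is made by a practised user and so does not count as a single lancing. Each incision is a single lancing, and nothing limits the primary objective to first use. Any learning would in any case affect the estimate, which is a separate question from interval width.
- One might conclude that the study is too small. With no target width stated, no printed figure is wrong and no shortfall can be shown.

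It is also fair that the size of the effect rests on an assumed ICC, that there is no loss at ICC 0, and that at ICC 0.3 and p = 50% the half-width changes by only 1.2 points (9.4 − 8.2). No success threshold is set that such a change could cross. The figures apply to pain only once a cut-off turns the 0–10 score into a proportion, and the protocol gives none.

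What the reply does not remove is the wording of Section 16.1 and the synopsis. Justification of the sample size belongs in the protocol, this one rests on interval precision, and it puts forward 100 paired draws with no allowance for the pairing. A later choice of analysis method would not correct that justification.

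**Conclusion.** The point holds in conditional form. Section 16.1 and the synopsis offer 100 draws as the basis for precision, although the design supplies 50 independent subjects. If the per-incision proportions are analysed as 100 independent results, the 90% intervals are too narrow by √(1+ICC). The loss lies between none (ICC 0) and the ceiling at ICC 1, where the half-width at p = 80%, for example, is 9.3 points instead of 6.6. The range rests on an ICC between 0 and 1, which is my assumption, and on a normal approximation that the simulation supports at ICC 0.5. It is a moderate matter, worth correcting before the data are analysed. It gives no ground for enlarging the study or doubting that it can be done.

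**What to change.** - **Section 16.1 and the synopsis.** Name the subject (n = 50) as the sampling unit, with two draws each. Replace the claim that 100 draws suffice with the achievable 90% half-width for an effective n between 50 and 100, giving the assumed proportion and ICC: 8.2 to 11.6 points at p = 50%, or 6.6 to 9.3 at p = 80%.
- **Section 16.3.** State the unit of analysis. For per-incision proportions, use an interval clustered by subject, such as a Wilson interval on the design-effect-adjusted n, or GEE with robust variance. Alternatively, report a subject-level proportion on n = 50 and say how a subject's two draws are combined.
- **Optional.** Report the proportion from the first incision only (n = 50) as a sensitivity analysis.

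The cost is a few sentences and slightly wider stated intervals. No further subjects, procedures or data are needed, because the case report form already records each incision separately.
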